Study Configuration	Mixed methods study with part one encompassing three qualitative focus group (FG) or interviews followed by a quantitative feasibility randomized control trial (RCT) with concurrent process evaluation.
Setting	Multicentre, Primary and secondary care services in Riyadh, Saudi Arabia.
Sample size estimate and Study Participants	Focus groups or interviews using purposeful sampling will comprise of 6–8 people with chronic non-specific low back pain, 6–8 physiotherapists and 6–8 orthopaedic surgeons (part I); 30 patients with chronic low back pain for the feasibility RCT (part II). There will be 38 to 44 study participants overall for part I and II. Process evaluation will include interviews with 4-6 patients and 2-4 healthcare practitioners.
Eligibility criteria	Part I: Participants with history for three months chronic non-specific low back pain whom are diagnosed with MRI from King Fahad Medical City. For the healthcare professionals, physiotherapists and orthopaedic surgeons who have experience in managing people with chronic low back pain in addition to having a privilege to request MRI for doctors. Part II: Participants over the age of 18 and below 65, of any gender, who have been diagnosed with chronic low back pain for more than 3 months
Description of Procedure	and didn't had physiotherapy treatment in the past 6 months. Part I: using FG method or interview, three FGs will be conducted with patients with chronic non-specific low back pain, orthopaedic surgeons and physiotherapists from King Fahad Medical City, Saudi Arabia. If FGs is not applicable, one- to-one interview will be conducted This will take place for approximately four months, following this study; the main psychosocial factors associated with MRI diagnosis will be identified. Part II: the psychosocial factors will be assessed on two randomized groups of patients; those who receive physiotherapy alone and those who had an MRI scan proceeding physiotherapy treatment. Following the trial, further interviews will be conducted with staff (Surgeons and physiotherapists and recruiting staff) in each site in the form of 'end of site meetings' to explore factors affecting recruiting and trial procedures.
Duration of study	Approximately 28 to 36 weeks. For part I, FG or interviews will run for 12 to 16 weeks. Part II, will require 16-20 weeks.

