The data from these focus groups or interviews will be analysed thematically to assist in identifying

the main psychosocial factors associated with diagnosing NS-CLBP patients using an MRI diagnosis.

Part II: Outcome measures will be selected according to the emerging themes from Part I.

Patients who meet the inclusion criteria will be randomly allocated to have an MRI scan

followed by physiotherapy or receive physiotherapy alone. A booklet of outcome measures

will be completed following consent and prior to randomization before physiotherapy and

repeated after physiotherapy treatment. Part II will be held in King Fahad Medical City.

Healthcare practitioners and patients with chronic low back pain and factors affecting trial

delivery will conduct process evaluation alongside the feasibility study to explore the

acceptance of randomisation.

STUDY MANAGEMENT

The chief investigator (CI), under the supervision of [name] and [name], will

be responsible for the management and progression of the study.

The methods of data collection are focus groups or interviews and questionnaires. In Part, FG, the

interviews or I will be audio recorded, after obtaining permission from each participant. The FG

usually takes 90 minutes for each group and they will be held at King Fahad Medical City. The CI will

contact candidate participants by telephone to arrange the time of the interview. After each FG or

interview, the audio recording will be evaluated to ensure that a good quality recording was obtained.

Then, the audio recording will be transcribed in verbatim and checked against the original audio

recording. Finally, the transcripts and the audio recording will be stored in a computer hard drive with

password protection.

In Part, II of the study, the themes that emerged from the interviews will be used to create a

booklet of outcome measures. The handbook will contain outcome measures of psychosocial

impairments with strong psychometric properties as well as modified questions, which are not

Page 13 of 28

The Psychosocial Impact of MRI Diagnosis in Chronic Non-Specific Low Back Pain

Study ID/ Psychosocial -Factors

covered by the outcome measure questionnaires. The time needed to fill in the booklet should

not exceed 20 minutes. This booklet of measures will be given to two groups of patients. The

first group will be patients who have had an MRI diagnosis for their back pain in the last

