month and the second group will be those who have not had an MRI scan. The outcome

measures booklet will be completed before starting and after finishing the physiotherapy

treatment.

The CI is responsible for all of the study management and is the data custodian as well.

DURATION OF THE STUDY AND PARTICIPANT INVOLVEMENT

The duration of the study will be approximately 28 to 36 weeks. Part I will require 12 to 16 weeks to

conduct the three focus group interviews, which will require additional time to arrange to

accommodate the professionals' busy schedules. Part II of the study will run for 16 to 20 weeks.

Additional process data collection will take place parallel to Part II and. Overall, the two parts of the

data collection will require 32 to 40 weeks.

End of the Study

The study will end after completing the last participant interview during the process evaluation.

ETHICAL APPROVAL

Ethical approval for this study will be sought from the Faculty of Medicine & Health Sciences

Research Ethics Committee (REC) and the local Ethics Committee at the hospital in Riyadh. Ethics

approval will also be sought from each hospital participating in this study.

Page 14 of 28

SELECTION AND WITHDRAWAL OF PARTICIPANTS

Recruitment

Part I: INTERVIEW STUDY

Recruitment of patient participants: [name] will obtain the ethical permission to

conduct the study from King Fahad Medical City. The physiotherapy team leader will invite the

patients who meet the inclusion criteria to a FG interview. Recruitment will take place in the

physiotherapy department. A consent form and patient information sheet will be given to the patients.

[name] will be responsible to answer any question participants may have before

signing the consent. A signature is required from each patient to document his/her acceptance to enrol

in the study. There will be six to eight patients, male and female without restriction in sex

representation.

Recruitment of clinician participants: [name] will obtain the ethical permission to

conduct the study from King Fahad Medical City. Physiotherapists and doctors who meet the inclusion

criteria will be invited to participate in a focus group. Physiotherapists and doctors will be invited by

the team lead. An ethical consent form and a participant information sheet will be given to the

participants. A signature is required from each participant to document his/her acceptance to enrol in

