the study. Each group will contain six to eight clinicians, male and female. If FG is not possible,

especially with physician, then one to one interview will be performed.

Part II:

In Part II of the study, [name] will approach the administrators at King Fahad Medical

City for approval to conduct the second part of the study. The lead physician will invite all patients

who met the inclusion criteria to take part in the study using the patients register program. An ethical

consent form and an information sheet will be handed to the patients. [name] will be

responsible to answer any question participants may have before signing the consent. A signature is

required from each patient to document his/her acceptance to enrol in the study. To ensure equal

distribution between groups, block randomization schedule will be used to assign patient into groups;

MRI group and control group. The MRI group will have MRI scan and discuss the result with their

doctors before having the physiotherapy treatment. The control group will have physiotherapy

treatment without MRI scan.

Process Evaluation:

Patient particepent of Part II, will be invited by email to participate in process evaluation interviews.

Additional consent forms and information sheets related to this study will be emailed to participants.

Reply from the participant with the approval is required t to document his/her acceptance to enrol in

the study. [name] will be responsible to answer any questions concerning these

documents.

The research team in King Fahad Medical City, including doctors and physiotherapists, will be invited

by email to participate in interview study to evaluate their experiences of the feasibility RCT. Mr

[name] will be responsible for contacting the research team and explaining the study aims.

For the focus groups and interviews:

Inclusion criteria:

Patient participants:

Male and female aged 18 to 65 years, CLBP with no clear medical diagnosis who had an MRI scan

and a report for LBP in the last month (e.g., malignancy, fracture, infection, spinal stenosis,

sponylosthesis or inflammatory disease). Chronicity will be considered if the pain has persisted for

more than three months.

Clinician participants:

Page 16 of 28

Physicians in direct contact with people with NS-LBP and with the authority to refer patients for MRI

will be recruited as clinician participants. Inclusion criteria for physiotherapists include outpatient

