physiotherapists with a primary interest in LBP management.

Exclusion criteria:

Women who are pregnant or less than six months postpartum, or have received pain-relieving

procedures (injection or denervation) in the previous three months or have evidence of neurological

impairment will be excluded from the study.

For the feasibility RCT:

Inclusion criteria:

Male or female aged 18 to 65 years; CLBP with no clear medical diagnosis who had an MRI scan and

a report for LBP in the last month (e.g., malignancy, fracture, infection, spinal stenosis, sponylosthesis

or inflammatory disease) will be included. Chronicity will be considered if the pain has persisted for

more than three months. Patients must not have had physiotherapy treatment in the six months prior to

the study.

Exclusion criteria:

Women who are pregnant or less than six months postpartum, or have received pain-relieving

procedures (injection or denervation) in the previous three months or have evidence of neurological

impairment will be excluded from the study.

Participant withdrawal

Participation in this study is voluntary. All participants are free to withdraw from the study at any

time, without fear of penalty of impact on their healthcare and the researcher could remove

participants from the study if needed as well. If there is a withdrawal from the study, the information

collected prior to the withdrawal will not be removed and shall be used in the analysis. The treatment

given to the patients will not be affected by their withdrawal from the study. Patients who drop out of

the study will not be replaced.

Page 17 of 28

The Psychosocial Impact of MRI Diagnosis in Chronic Non-Specific Low Back Pain

Study ID/ Psychosocial -Factors

Informed consent

The consent form must be signed and dated prior to participating in the study. The CI will explain the

study by providing an information sheet and answering the questions of the patients and clinicians.

Both healthcare practitioners and patients will be contacted during and after the feasibility trial asking

if they would be willing to take part in an interview at the end of the trial, about their experiences of

taking part in the trial, the process of the trial and factors affecting its delivery.

STUDY REGIMEN

Compliance

Participation in the FG and the returned handbook of outcome measures are the indictors for

compliance.

Criteria for terminating the study

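### The RCT inclusion criteria require a recent MRI scan and report of every patient, which contradicts the randomised comparison with physiotherapy without MRI

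*Protocol*

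**What the plan says.** All references are to the protocol; no SAP is at hand.

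- **For the feasibility RCT, Inclusion criteria.** The criterion opens "Male or female aged 18 to 65 years; CLBP with no clear medical diagnosis who had an MRI scan and". It goes on to require a report within the past month and then gives a bracketed list of pathologies. The condition applies to everyone enrolled.
- **For the focus groups and interviews, Inclusion criteria (Part I).** Nearly the same sentence appears: "Male and female aged 18 to 65 years, CLBP with no clear medical diagnosis who had an MRI scan", again with a report in the past month.
- **Study Configuration, Part II.** Eligibility comes before allocation: "Patients who meet the inclusion criteria will be randomly allocated to have an MRI scan". Physiotherapy comes next in that arm, and the other arm gets physiotherapy alone. The outcome booklet is first completed after consent and before randomisation.
- **Recruitment, Part II.** The arms are described thus: "MRI group and control group. The MRI group will have MRI scan and discuss the result with their". In that arm the discussion is with the patient's doctor and precedes physiotherapy; controls get physiotherapy with no scan.
- **Study Management.** One group is described as patients whose back pain was imaged by MRI within the past month. Of the other it says: "the second group will be those who have not had an MRI scan".
- **Synopsis, Eligibility criteria.** The entry begins "Part II: Participants over the age of 18 and below 65, of any gender, who have been diagnosed with chronic low back pain". It adds a minimum duration of three months and no recent physiotherapy. MRI is not mentioned for Part II.
- **Sample size and justification.** The target is 30 patients, 15 per arm.

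**The concern.** The trial is meant to randomise patients between having an MRI before physiotherapy and not having one. A criterion that admits only recently scanned patients puts the exposure of interest into both arms before randomisation.

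The main quantitative objective is whether patients and physicians accept randomisation to these two groups, together with the recruitment rate and the reasons for non-recruitment. A patient who already holds a recent report and is asked to forgo a second scan faces a different decision from one asked to go without any scan. Rates from the first kind of patient do not carry over to a definitive trial in the second kind. The objective of sizing that trial suffers too, because the baseline booklet would no longer record psychosocial state before an MRI diagnosis.

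**Working it through.** **1. Side-by-side reading.** The RCT inclusion criteria and the group description in Study Management cannot both hold. The first requires an MRI and report in the past month of every patient; the second describes a group without an MRI. The set of patients satisfying both is empty. Study Configuration and Recruitment apply the criteria before allocation, so the conflict cannot be settled by saying that the MRI requirement concerns one arm only.

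**2. Prior exposure by arm.** Inputs: 15 per arm (Sample size and justification) and the criterion as written. Let q be the share of controls who hold a recent MRI report. Every MRI-arm patient has one by the time physiotherapy starts, so the contrast in having a recent MRI diagnosis is 1 − q.

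| Reading of eligibility | Controls with recent MRI | Contrast |
|---|---|---|
| RCT criterion applied literally | 15/15 (q = 1) | 1 − 1 = 0 |
| Half of controls scanned (illustrative) | q = 0.5 | 1 − 0.5 = 0.5 |
| Controls unscanned, as Study Management describes | 0/15 (q = 0) | 1 − 0 = 1 |

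This restates the criterion in numbers and is not independent evidence. It concerns exposure to a recent MRI diagnosis. The randomised contrast under the literal reading is not empty: one arm gets a further scan and a discussion of its result, and the other gets neither.

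**3. Baseline timing.** The booklet is completed before randomisation. Under the literal criterion, that point lies after an MRI report for all 30 patients, so no pre-MRI measurement exists in either arm.

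**4. Recruitment estimate.** Inputs from Sample size and justification: 80 patients per clinic per month, two clinics, six weeks, two thirds ineligible, half of the rest refusing.

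- At 4 weeks per month: 80 × 2 × (6/4) × 1/3 × 1/2 = 40.
- At 52/12 = 4.33 weeks per month: 80 × 2 × (6/4.33) × 1/3 × 1/2 = 36.9.

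Neither gives 30. The protocol calls 30 a realistic target and does not present it as this product, so the difference is not an error. The calculation does show the available slack. If a further share r of otherwise eligible attendees were excluded as recently scanned, the yield would be 40(1 − r) or 36.9(1 − r). It stays at 30 or more while r ≤ 1 − 30/40 = 0.25, or r ≤ 1 − 30/36.9 = 0.19. The protocol does not say whether its two-thirds figure already reflects any MRI condition, and it gives no value for r.

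**The case against.** The best defence is that the intent is plain. Study Configuration and Recruitment both describe random allocation to MRI or no MRI, Study Management refers to unscanned patients, and the synopsis asks for no MRI. A sensible site would see that the RCT sentence is misplaced. This stands in part: the contrast is lost only if that sentence is applied literally. It does not remove the problem. The sentence is in the section against which patients are screened, and a site that follows the evident intent would enrol patients who fail a written inclusion criterion.

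Four stronger readings are tempting, and the documents do not support them.

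- **That Study Management sets up a non-randomised comparison by MRI history.** Its wording is loose and fits poorly with a baseline before randomisation, but it can be read as describing the randomised groups after allocation. The synopsis uses a similar past tense for groups that it explicitly calls randomised.
- **That the synopsis is a further conflicting version.** It is a summary that is silent on MRI. Silence can coexist with a fuller criterion.
- **That the trial would compare nothing, or could show nothing about feasibility.** A repeat scan with discussion against neither is still a contrast, though not the intended one. Attrition and aspects of protocol integrity could still be observed.
- **That the criterion was certainly copied from Part I.** The near-identical wording makes this likely, but it remains an inference, and the point does not depend on it.

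**Conclusion.** The concern holds as an internal contradiction that must be resolved before recruitment. As written, the RCT eligibility section requires of every patient the exposure that the control group is meant not to have, and no other section overrides it.

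The consequence depends on literal application. In that case all 15 controls have had a recent MRI and report, the contrast in recent MRI diagnosis falls from 100 percentage points to 0, and baseline follows an MRI report in both arms. What remains is a randomised comparison of a repeat scan plus discussion with no repeat scan. Acceptance of randomisation and the recruitment rate are the objectives most affected, since they would describe already scanned patients. The conclusion assumes only that the criteria apply to both arms before allocation, as Study Configuration and Recruitment state.

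**What to change.** 1. In the RCT inclusion criteria, remove the requirement for a prior MRI scan and report. Reconcile this section with Study Configuration, Study Management and Recruitment so that controls are patients without a recent MRI diagnosis. The look-back period is for the investigators to set; the documents give no basis for choosing one here.
2. Reword the bracketed list of pathologies so that it is clear these are examples of diagnoses that rule a patient out. At present the list follows the mention of the MRI report and can be misread.
3. In Study Management, define the two groups by randomised allocation and not by MRI history.
4. Recheck the two-thirds-ineligible assumption in Sample size and justification against the corrected criteria.

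The cost is a wording change and a screening question on recent MRI. It is cheapest before ethics approval, because the protocol says that a later modification needs a full review of all documents. The downside is that recently scanned attendees become ineligible, which may slow accrual. On the protocol's own figures, the six-week plan could absorb the loss of about 19% to 25% of otherwise eligible attendees before falling below 30, provided that the two-thirds figure does not already include them.

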SIGNATURE PAGES	25
Reference	27

STUDY BACKGROUND INFORMATION AND RATIONALE

Low back pain (LBP) is one of the most prevalent musculoskeletal disorders in industrialized societies

(Kelsey et al., 1979, Haddad, 1987). Although the prevalence of LBP is high, with up to 80% of

people reporting at least one episode during their lifetime (Leboeuf-Yde et al., 1997), most recover

within one month (Jarvik and Deyo, 2002). However, between 10 and 40% of all LBP patients fail to

recover, and go on to develop chronic symptoms and live with some form of disability. Of these

patients, 85% are reported to have non-specific chronic LBP (NS-CLBP) in which a specific diagnosis

using radiological imaging cannot be found (Leboeuf-Yde et al., 1997, Jarvik and Deyo, 2002).

Magnetic resonance imaging (MRI) is one of the most advanced imaging techniques available for

investigating LBP. Since MRI is demonstrably superiority in detecting pathology to other techniques

for imaging the lumbar spine anatomy, it is the preferred method for detecting pathological conditions

such as neoplasm, metabolic disorders and degeneration (Borenstein et al., 2001).

Despite the accuracy of lumbar spine MRI and its preferred use in the identification of specific

pathologies, false positive findings have been reported in the lumbar spines of asymptomatic

individuals (Jarvik et al., 2005). In one study, 52% of an asymptomatic population was found to have

disc bulges and 27% had disc protrusions (McCullough et al., 2012). These abnormalities did not

predict LBP after a follow-up period of seven years (Modic et al., 2005). In another trial, 76

asymptomatic people underwent MRI scan and revealed no abnormalities in 50% of the subjects with

LBP (Boden et al., 1990).

A recent systematic literature review of articles published about the prevalence of MRI finding in

asymptomatic people (Brinjikji et al., 2015) indicated that the likelihood of detecting degeneration in

asymptomatic individuals is proportional to age, meaning that it is part of the normal aging process.

Since abnormalities can range from disk bulging or herniation, annular fissure and degenerative disk

disease, many changes observed using MRI may be coincidental or unrelated to the patient's

presenting symptoms. Based on the existing literature, the clinical application of MRI in CLBP is

therefore unclear.

Page 8 of 28

Although, in all LBP guidelines, a consensus exists MRI scan does not add a value in diagnosing NS-

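### The RCT inclusion sentence requires a recent MRI, which contradicts randomising to MRI or no MRI, and its misplaced list of pathologies leaves unclear whether suspected specific disease is excluded.

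*Protocol*

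**What the plan says.** **RCT inclusion** (Protocol, Selection and Withdrawal of Participants, For the feasibility RCT). The criterion begins "Male or female aged 18 to 65 years; CLBP with no clear medical diagnosis who had an MRI scan and". It then adds the MRI report and the list: "a report for LBP in the last month (e.g., malignancy, fracture, infection, spinal stenosis, sponylosthesis". The sentence closes, and the next one opens, with "or inflammatory disease) will be included. Chronicity will be considered if the pain has persisted for". The duration set is over three months. Physiotherapy in the previous six months is also ruled out.

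**RCT exclusion** (same section). The sentence opens "Women who are pregnant or less than six months postpartum, or have received pain-relieving". It goes on to rule out patients with recent injections or denervation and those with signs of neurological impairment. No other condition is named.

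**Allocation** (Recruitment, Part II). Block randomisation is used, and the arms are described as "MRI group and control group. The MRI group will have MRI scan and discuss the result with their". That discussion is with the patient's physician and precedes physiotherapy. Controls receive physiotherapy without a scan. The lead physician invites everyone on the patient register who meets the inclusion criteria.

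**Groups** (Study Management). The first group has had an MRI diagnosis within the last month. The second has not had a scan.

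**Synopsis, Eligibility criteria, Part II.** Adults "who have been diagnosed with chronic low back pain for more than 3 months" with no recent physiotherapy. There is no mention of MRI, of non-specific pain or of any pathology to be ruled out.

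**Background.** Of MRI, the Protocol says that "for imaging the lumbar spine anatomy, it is the preferred method for detecting pathological conditions", giving neoplasm, metabolic disorders and degeneration as examples.

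**The concern.** Recruiting staff have to apply this sentence, because the physician invites whoever satisfies it. As worded, it does not say which patients may be randomised.

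Three things are at stake:

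- **The contrast.** If a scan and report from the last month are needed for entry, both arms have already received the exposure that the trial sets out to compare.
- **The population.** The study question concerns non-specific pain. The conditions that make pain specific appear only inside a sentence about who is included.
- **Patients with suspected disease.** The absence of a clear diagnosis depends on what has been established so far. It does not address a patient in whom a physician suspects one of the listed conditions but has not confirmed it. If such a patient enters without a prior scan, allocation decides whether the trial provides one.

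The Adverse Events section says that no such data will be collected, so a missed pathology among controls would not be captured as an adverse event.

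**Working it through.** The faults lie in the wording, and the plan states no figure to reproduce. The check sets the sections side by side.

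**Step 1: what the list modifies.** In the inclusion sentence the parenthesis follows the MRI report, so grammatically the six conditions are examples of reports. Their evident purpose is to illustrate the clear diagnosis that must be absent. The Part I patient criteria (For the focus groups and interviews) have the same parenthesis in the same position, which suggests that the text was carried over.

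**Step 2: whether another section repairs it.** The exclusions cover pregnancy and the postpartum period, recent pain-relieving procedures, and neurological impairment. I take the last two to apply to both sexes, although the grammatical subject of the sentence is women. None of the six conditions appears there, and no other screening step for them is described.

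**Step 3: prior MRI against the design.**

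| Section | MRI status at entry |
|---|---|
| RCT inclusion criterion | Scan and report in the last month required |
| Study Configuration, Part II | Not stated; scan then physiotherapy, or physiotherapy alone, is allocated at random |
| Recruitment, Part II | Not stated; the scan follows allocation to the MRI group, and controls are treated without one |
| Study Management | First group scanned in the last month, second group not scanned |
| Synopsis, Part II | No requirement |

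Taken literally, the inclusion criterion leaves no eligible patient for the second group described under Study Management. Randomisation could then only assign a repeat scan or none. The baseline booklet, completed after consent and before randomisation, would follow an MRI report in every patient. For Part I the clause makes sense, because those patients are interviewed about a scan they have had. For Part II it does not fit.

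**Step 4: setting the prior-MRI clause aside, as the design requires.** Two stated filters bear on specific disease: no clear diagnosis, and no evidence of neurological impairment. A patient with suspected but unconfirmed pathology and no neurological signs passes both and may be allocated to control.

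**Step 5: how often.** The documents give no rate. As an illustration only, assume that a share p of those enrolled are such patients.

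- Expected number among 30: 30 × p. For p = 1%, 0.3; for p = 5%, 1.5.
- Chance of at least one among 15 controls: 1 − (1 − p)^15. For p = 1%, 1 − 0.99^15 = 0.14; for p = 5%, 1 − 0.95^15 = 0.54.

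The range comes entirely from the assumed p. The Background reports that 85% of chronic cases are non-specific, but the remaining 15% does not supply p. It counts all specific back pain, before either filter and whether or not already diagnosed.

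**The case against.** The strongest reply is that the criterion itself prevents the harm. Anyone who satisfies it word for word has been scanned and reported within the last month and still has no clear diagnosis. One cannot read the list literally and ignore the MRI clause in the same sentence. This stands: a reader might infer that the inclusion criterion, as written, lets an unscanned patient with suspected disease be randomised to no MRI, and it does not. That outcome arises only once the clause is dropped. The reply does not rescue the sentence, because keeping the clause defeats the randomised comparison.

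Other replies also have force:

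- **Known pathology.** A reader might infer that confirmed malignancy or fracture is eligible. On any sensible reading, the requirement of no clear diagnosis bars it.
- **Other safeguards.** The neurological-impairment exclusion removes some suspected cases, and the researcher may remove participants if needed. Neither is a screen for the listed conditions.
- **Background.** A reader might infer that the Protocol calls MRI the preferred test for all six conditions. Of its three examples only neoplasm matches the list, although the examples are not exhaustive.
- **Synopsis.** The title, first synopsis objective and purpose all say non-specific. The shorter Part II wording is a lapse, not evidence that a wider population is intended.
- **Physician acceptance.** Ambiguous eligibility might affect physicians' willingness to randomise, which is part of the primary feasibility objective. Nothing in the documents shows that it would.

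**Conclusion.** The inclusion sentence for the RCT is wrong as written and should be corrected. The contradiction over prior MRI is a matter of text, needs no assumption, and bears on the entry of all 30 participants. The misplacement of the pathology list and the silence of the exclusions are equally plain.

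The consequence for patients is conditional. If the prior-MRI clause is inoperative, as the rest of the design implies, a patient with suspected but unconfirmed specific pathology could be allocated to the no-MRI arm. How often cannot be sized from the documents. The 14% to 54% shown above must not be read as an estimate of risk, since it only restates an assumed 1% to 5%.

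The documents do not support saying that the trial intends to enrol patients with specific disease, or that the criterion taken literally denies them imaging. Whether suspected cases should be excluded is a clinical decision for the investigators. The finding is that the Protocol does not state it.

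**What to change.** Reconcile the Synopsis (Eligibility criteria, Part II), Study Configuration, Study Management, Recruitment (Part II) and the RCT criteria in one amendment:

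1. State whether a prior MRI is required for RCT entry or incompatible with it, and over what period. Make the description of the two groups agree.
2. Take the list of conditions out of its place after the MRI report and attach it to the diagnoses that must be absent. Moving the list alone is not enough, because the sentence would still demand a recent scan.
3. Have the investigators state whether suspected as well as known cases are excluded, and record the answer for each patient before randomisation.
4. Add non-specific to the Part II line of the synopsis.

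The cost is protocol wording, one screening item and ethics committee review, since the Protocol says that modification after approval requires a full review. The eligible pool may shrink slightly. The Protocol's own recruitment assumptions leave some room: 80 per clinic per month × 2 clinics × 1.5 months × 1/3 eligible × 1/2 consenting = 40, against a target of 30. Taking six weeks as 6 × 12/52 = 1.38 months gives 37.
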